### Schedule of Assessments (cont.)

Week	Day	Treatment Period								
		-4 to 0	1	2	4	12	24	26	36	52/ET
	-28 to -1	1 a	15	28	84	168	182	252	364	
Concomitant medications		X	X	X	X	X	X	X	X	
Study drug infusion			X s	X s			X s	X s		
Corticosteroid dose/taper t			X	X	X	X				
Renal biopsy (optional) u									(x)	

ADA=anti-drug antibody; ET=Early Termination Visit; HBcAb=hepatitis B core antibody; HBsAg=hepatitis B surface antigen; HBV=hepatitis B virus; IV=intravenous; IxRS=interactive voice/Web response system; PK=pharmacokinetic; PO=by mouth; SLEDAI-2K=Systemic Lupus Erythematosus Disease Activity Index; SLICC/ACR=Systemic Lupus International Collaborating Clinics/American College of Rheumatology.

Notes: All assessments will be performed pre-infusion unless otherwise specified. Infusion visits (Days 15, 168, and 182) except for Day 1, should be performed within  $\pm$  3 days of the scheduled visit. Non-infusion visits should be performed within  $\pm$  3 days of the scheduled visit.

- a Day 1, unless otherwise notified.
- b At screening, IxRS will be contacted to obtain assignment of patient screening number. At Day 1, IxRS will be contacted to obtain patient randomization number and drug assignment.
- c Subject's Global Assessment will be performed prior to other assessments.
- d Blood pressure and pulse rate while patient is seated for 5 minutes, and respiratory rate and body temperature. Vital signs should be taken pre-infusion, then every 15 minutes for 1 hour, then every 30 minutes until the end of the infusion, and within 30 minutes post-infusion. Additional readings may be obtained at the discretion of the investigator in the event of an infusion-related reaction (e.g., hypotension and/or fever).
- e If a chest X-ray has been obtained within the past 3 months and no clinically significant abnormality was observed and no new pulmonary signs or symptoms are exhibited, no chest X-ray is required.
- f Hematology: CBC, RBC count, WBC count and differential, hemoglobin, hematocrit, mean corpuscular volume, mean corpuscular hemoglobin, and quantitative platelet count.
- g Serum chemistries include AST/SGOT, ALT/SGPT, alkaline phosphatase, total protein, albumin, cholesterol, total bilirubin, BUN, uric acid, creatinine, random glucose, lactate dehydrogenase, potassium, sodium, chloride, calcium, phosphorus, CPK, and triglycerides. At screening and at unscheduled visits, amylase and lipase will be also included.

## Appendix 1

### Schedule of Assessments (cont.)

- h All urinalyses must include microscopic examination, macroscopic urinalysis, and spot urine protein to creatinine ratio (preferably done on the first morning urine). The spot urine protein to creatinine ratio on Days 1, 84, 168, 252, and 364 must be done from first-morning urine.
- i To be analyzed for total protein, total creatinine, creatinine clearance, and protein to creatinine ratio.
- j For women of childbearing potential, including those who have had a tubal ligationPositive test results will be confirmed with a serum pregnancy test. Study drug infusion must not be administered unless the pregnancy test result is negative.
- k Patients who are HBsAg negative and HBcAb positive with no detectable DNA will be allowed into the study but will require regular monitoring of HBV DNA (see the Laboratory Manual for further details).
- l Autoantibodies include anti-nuclear antibody, anti-dsDNA, Sm, Ro, La, RNP, and anti-C1q.
- m Antibody titers include mumps, rubella, *Varicella*, tetanus, influenza, and *S. pneumoniae*.
- n Obtain pre-infusion (within 30 minutes prior to the start of infusion) and at the end of infusion (or within 30 minutes after the end of infusion).
- o Samples will be drawn before administration of study drug on dosing days.
- p Urine for biomarkers will be processed at the study site. Instructions will be provided in the laboratory manual.
- q The DNA samples are optional and should only be obtained from patients who sign the separate Roche Clinical Repository Informed Consent Form. Preferably, samples will be obtained at screening visit, but they may be obtained at subsequent study visits.
- r On Day 1, adverse events will be recorded during infusion and post-infusion. For Days 15, 168, and 182, adverse events will be recorded pre-infusion, during infusion, and post-infusion. For all serious infectious adverse events reported, CBC with differentials, quantitative Ig, and CD19 B-cell counts should be determined within 1 week of onset.
- s On Days 1, 15, 168, and 182, administer 80 mg methylprednisolone IV (or placebo), 650–1000 mg acetaminophen PO, and 50 mg diphenhydramine PO (or other antihistamine) 30–60 minutes prior to the study-drug infusion.
- t Patients may initiate 0.5 mg/kg/day oral prednisone in screening or at Day 2. Oral corticosteroid taper will begin on Day 16. The maximum allowable daily dose of prednisone will be 60 mg.
- u All patients will be asked to undergo an optional repeat renal biopsy after completion of the treatment portion of the study (after Week 52). If a patient agrees to a repeat renal biopsy, one should be performed within 4 weeks of completion of the treatment portion of the study. Biopsies performed at other times, for clinical reasons, will also be submitted for central review. Because examination of the biopsy sample may potentially unblind the study treatment, investigators and study site personnel should not examine the biopsy sample for immunohistochemistry of B cells or be informed of its results.

## Appendix 2

### Follow-Up and B-Cell Follow-Up Assessments

Evaluation/Procedure	Follow-Up		B-Cell Follow-Up
Week	76	104	Every 6 Months
Study Day ( $\pm$ 7 days)	532	728	
SLICC/ACR		x	
Serum chemistries a	x	x	x
Urinalysis b	x	x	x
Urine chemistries: P/C b	x	x	x
Pregnancy test c	x	x	x
Autoantibody profile d	x	x	x
Blood sample for flow cytometry		x	x
Serum ADAs	x	x	x
Serum pharmacokinetics	x	x	x
Quantitative serum Ig levels (total, IgG, IgM, and IgA)	x	x	x
PAXgene RNA	x	x	x
Urine for biomarkers e	x	x	x
Serum for biomarkers	x	x	x
Plasma for biomarkers	x	x	x
Adverse events f	x	x	x
Glucocorticoid Toxicity Change Index	x	x	
Concomitant medications	x	x	x

ADA=anti-drug antibody; P/C=protein to creatinine ratio; SLICC/ACR=Systemic Lupus International Collaborating Clinics/American College of Rheumatology.

Note: All urine tests should be performed on first-morning urine.

a Serum chemistries include AST/SGOT, ALT/SGPT, alkaline phosphatase, total protein, albumin, cholesterol, total bilirubin, BUN, uric acid, creatinine, random glucose, lactate dehydrogenase, potassium, sodium, chloride, calcium, phosphorus, CPK, and triglycerides.

b Microscopic and macroscopic.

c For women of childbearing potential, including those who have had a tubal ligation. Urine pregnancy test on Weeks 76 and 104. If result of urine pregnancy test is positive, confirm with a central laboratory serum pregnancy test.

d Autoantibodies include: ANA, dsDNA, Sm, Ro, La, RNP, anti-c1q

e Urine for biomarkers will be processed at the study site. Instructions will be provided in the laboratory manual.

f For all serious infectious adverse events reported, CBC with differentials, quantitative Ig, and CD19 B-cell counts should be determined within 1 week of onset.

**Appendix 3 International Society of Nephrology/Renal Pathology Society (ISN/RPS)  
2003 Classification of Lupus Nephritis**

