### LENGTH OF STUDY

The study will follow all patients for a minimum of 78 weeks after the last infusion of obinutuzumab at Day 182. In consideration of recruitment and follow-up (independent of B-Cell follow-up [BCFU]), the length of study is estimated to be greater than 36 months. Patients may enter BCFU and continue to be evaluated for safety on a limited basis.

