### END OF STUDY

The end of this study is defined as the last patient's last visit at Week 104. This has been selected to enable 78 weeks (~18 months) of safety follow-up after the last dose of study drug to assess the occurrence of adverse events and to enable an assessment of peripheral blood CD19+ B cell return.

Additional B-cell follow-up (BCFU) visits will occur until patients have achieved their baseline CD19+ count or achieved 25 cells/ $\mu\text{L}$  CD19+ count (the lower limit of normal (LLN) of CD19+ B cells for this lupus population), whichever occurs first. B-cell follow-up (BCFU) visits for all patients will end when the last patient has completed ~18 months of safety follow-up from the last dose of blinded obinutuzumab infusion.

Patients who receive additional therapies that reduce peripheral B-cell counts will not be included in BCFU.

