### **2.2 SAFETY OBJECTIVES**

The safety objectives for this study are as follows:

- To evaluate the safety of obinutuzumab compared with placebo in patients with Class III or IV LN, focusing on the nature, frequency, and severity of serious and non-serious adverse events, as well as effects on laboratory values, vital signs, or other safety biomarkers
- To characterize the immunogenic potential of obinutuzumab by measuring human anti-drug antibodies (ADAs) and assessing their relationship with other outcome measures
- To fully characterize adverse events of special interest, including infusion reactions, infections, thrombocytopenia, and neutropenia

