### **3.2 END OF STUDY**

*The end of this study is defined as the last patient's last visit at Week 104. This has been selected to enable 78 weeks (~18 months) of safety follow-up after the last dose of study drug to assess the occurrence of adverse events and to enable an assessment of peripheral blood CD19+ B cell return.*

*Additional B-cell follow-up (BCFU) visits will occur until patients have achieved their baseline CD19+ count or achieved 25 cells/µL CD19+ count (the lower limit of normal (LLN) of CD19+ B cells for this lupus population), whichever occurs first. B-cell follow-up (BCFU) visits for all patients will end when the last patient has completed ~18 months of safety follow-up from the last dose of blinded obinutuzumab infusion.*

*Patients who receive additional therapies that reduce peripheral B-cell counts will not be included in BCFU.*

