### **3.4.2 Safety Outcome Measures**

The safety outcome measures for this study are as follows:

- Incidence, type, and severity of adverse events
- Abnormal vital signs
- Abnormal laboratory values

Safety will be monitored through regular physical examinations, vital signs, hematologic and chemistry laboratory tests, urinalyses, and incidence and severity of adverse events. In addition, the following will be examined:

- Circulating B cells, T cells, neutrophils and other cell populations
- Plasma immunoglobulins (total Ig, IgG, IgM, and IgA)

- Record of menses
- Pregnancy
- Antibody titers for mumps, rubella, *Varicella*, tetanus, influenza, and *Streptococcus pneumoniae*

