**Table 6 Guidelines for Management of Specific Adverse Events (cont.)**

Event	Action to Be Taken
Infections: suspected PML	
 
Stop study drug.
 
Obtain neurological consult.
 
In consultation with a neurologist, we recommend obtaining an MRI and performing a lumbar puncture to assess for CSF JC viral DNA.
 
Notify monitors immediately.
 
Study treatment will be withheld for all participants while patient is unblinded and investigated for suspected PML.
 

Neutropenia	
 
Patients who experience neutropenia should be closely monitored with regular laboratory tests until resolution.
 
If treatment is necessary, it should be administered in accordance with local guidelines and administration of granulocyte colony stimulating factors should be considered.
 
Any signs of concomitant infection should be treated as appropriate.
 
Grade 3 or 4 neutropenia that does not resolve to Grade <math>\leq 2</math> within 8 weeks is a treatment-discontinuation criterion.
 
Cases of late onset neutropenia (occurring 28 days after the end of treatment) or prolonged neutropenia (lasting more than 28 days after treatment has been completed/stopped) have also been reported in studies of obinutuzumab for hematologic malignancy.
 

Thrombocytopenia	
 
Patients should be closely monitored for thrombocytopenia.
 
If thrombocytopenia occurs, regular laboratory tests should be performed until the event resolves, and dose delays should be considered in case of severe or life-threatening thrombocytopenia.
 
Transfusion of blood products (i.e., platelet transfusion) according to institutional practice is at the discretion of the treating physician.
 
Thrombocytopenia that does not resolve to Grade <math>\leq 2</math> within 8 weeks is a treatment-discontinuation criterion.
 
Use of all concomitant therapies, which could possibly worsen thrombocytopenia related events such as platelet inhibitors and anticoagulants, should also be taken into consideration
 

Hypogammaglobulinemia	
 
Ig levels will be monitored throughout the study period.
 
IVIG should be considered for patients with recurrent/severe infections despite appropriate treatment, with concomitant hypogammaglobulinemia.
 

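### No blood count is scheduled after Week 52, so laboratory-based neutropenia and thrombocytopenia cannot be assessed systematically in 52 of the 78 post-dose weeks or in B-cell follow-up

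*Protocol*

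**What the plan says.** **Aims.** Protocol Section 2.2 lists as a safety objective: "To fully characterize adverse events of special interest, including infusion reactions, infections, thrombocytopenia, and neutropenia". Section 3.4.2 states: "Safety will be monitored through regular physical examinations, vital signs, hematologic and chemistry laboratory tests". It also names neutrophils among the cell populations to be examined, as does SAP Section 2.2.4. Section 5.2.3 makes drug-related neutropenia and drug-related thrombocytopenia adverse events of special interest.

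**Length of follow-up.** The synopsis says: "The study will follow all patients for a minimum of 78 weeks after the last infusion of obinutuzumab at Day 182". On the Week 104 end point, Section 3.2 says: "This has been selected to enable 78 weeks (~18 months) of safety follow-up after the last dose of study drug".

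**Where counts are scheduled.** The treatment-period schedule (Protocol Appendix 1, repeated as SAP Appendix 2) carries the panel: "Hematology: CBC, RBC count, WBC count and differential, hemoglobin, hematocrit, mean corpuscular volume, mean corpuscular hemoglobin, and quantitative platelet count". The last visit in that schedule is Week 52. Protocol Appendix 2 covers Week 76, Week 104 and six-monthly B-cell follow-up. It lists chemistries, urinalysis, immunoglobulins, drug levels, anti-drug antibodies and biomarkers, but no hematology. Its only blood count is the one triggered by infection: "For all serious infectious adverse events reported, CBC with differentials, quantitative Ig, and CD19 B-cell counts should be determined within 1 week of onset". Flow cytometry at Week 104 and in B-cell follow-up covers B, T and NK cells (Section 4.5.8), so it gives neither neutrophils nor platelets.

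**Known risk.** Protocol Table 6 records from studies in hematologic malignancy: "Cases of late onset neutropenia (occurring 28 days after the end of treatment) or prolonged neutropenia".

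**Analysis.** SAP Section 4.8 accumulates safety outputs to final lock and adds a separate summary of key outputs after Week 104. Section 4.8.2 gives rates per 100 patient-years for key safety events. Section 4.8.4.1 plans shift tables from baseline to the highest post-baseline grade for certain tests. The SAP does not name these events and tests.

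**The concern.** The follow-up was lengthened for safety, but the measurement that defines two of the named events stops a third of the way through it. An asymptomatic low neutrophil or platelet count after Week 52 will be found only if someone has another reason to take blood. Three consequences follow for the final report.

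- Time without routine counts can enter a rate denominator, while asymptomatic events from that time mostly cannot enter the numerator. The highest-grade tables have the same weakness: a patient with no later count looks like a patient with no later abnormality.
- Counts taken because of serious infection are a selected sample. They would distort any description of how cytopenia and infection relate. If serious infections differ between arms, so would the chance of detecting cytopenia.
- The separate post-Week-104 safety summary covers a period with no scheduled count, so few cytopenias there could reflect few tests.

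**Working it through.** **Inputs.** Last infusion Day 182, Week 36 = Day 252 and Week 52 = Day 364 (Protocol Appendix 1); Week 76 = Day 532 and Week 104 = Day 728 (Protocol Appendix 2). Week 52 is taken as the last hematology visit, as the SAP's copy of the schedule shows. The protocol table as extracted has one mark fewer in that row. If counts really ended at Week 36, the gap would be (728 − 252)/7 = 68 weeks.

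**The plan's own figure.** (728 − 182)/7 = 78.0 weeks, which matches the stated 78.

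**Split of the 78 weeks**
- Through the last scheduled count: (364 − 182)/7 = 26.0 weeks, with counts on Days 252 and 364.
- With no scheduled count: (728 − 364)/7 = 52.0 weeks; 52/78 = 66.7%.
- B-cell follow-up time is additional.

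**Late-onset neutropenia.** Table 6 places onset 28 days after the end of treatment: 182 + 28 = Day 210. The Day 252 and Day 364 counts therefore cover the early part of the late-onset period.

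**Reporting periods for adverse events of special interest**
- Section 5.3.1 reports all adverse events to Week 104 or 76 weeks after the last dose, whichever is longer. The second limit is 26 + 76 = Week 102, so Week 104 applies.
- Section 5.4.2.2 reports serious events and events of special interest for 52 weeks after the last dose: 26 + 52 = Week 78.
- On the second reading, the special-interest period without a scheduled count is 78 − 52 = 26 weeks. On the first it is 52 weeks.

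**Worst-case effect on a rate.** Suppose 120 patients, no dropout, no cut at rescue, a constant hazard, an illustrative true rate of 10 per 100 patient-years and no detection at all after Week 52. Patient-time to Week 104 is 120 × 2 = 240 patient-years, of which 120 fall before Week 52. Detected events are 10 × 120/100 = 12, and the reported rate is 12/240 × 100 = 5. With any later detection, the figure lies between 5 and 10. This is a bound; the documents supply no cytopenia rate.

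**With hematology at Weeks 76 and 104.** Scheduled post-dose counts rise from 2 to 4. The gaps become (532 − 364)/7 = 24 and (728 − 532)/7 = 28 weeks, so the longest falls from 52 to 28 weeks.

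**The case against.** A reader might infer that late cytopenias cannot be characterised at all, or that the infection footnote is the only route to a count. The documents do not support either reading.

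- Adverse events are collected at Week 76, Week 104 and in B-cell follow-up. Section 5.3.5.5 makes an abnormal count reportable when it is symptomatic, treated or judged clinically significant.
- Table 6 requires regular laboratory tests until a known neutropenia or thrombocytopenia resolves.
- Section 4.5.8 allows hematology samples for mycophenolate safety monitoring, and Section 4.4.1.2 keeps patients on background immunosuppression for a time after Week 52.

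These points stand. They do not restore systematic ascertainment. The monitoring samples have no timetable, and mycophenolate may be reduced, switched or withdrawn after Week 52. Appendix 4 asks for some low counts to be rechecked at the next scheduled visit, but after Week 52 those visits include no count.

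A reader might also infer that reported rates will be halved. The SAP does not establish this. Section 4.8.2 names no cytopenia rate and bases its rates on adverse event occurrences. Section 4.8 stops the main safety analyses at non-corticosteroid rescue. Section 4.5 confines by-visit displays to scheduled visits, so by-visit hematology already ends at Week 52. With equal follow-up and equal detection by arm, the ratio between arms would not change.

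Finally, the synopsis says safety evaluation in B-cell follow-up is limited, so a lighter schedule there was intended. That explains the B-cell follow-up column better than it explains Weeks 76 and 104, which belong to the 78 weeks chosen for safety.

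**Conclusion.** The point holds as a gap in systematic measurement. For a patient last dosed on Day 182, no blood count is scheduled in 52 of the 78 post-dose weeks (67%) or in B-cell follow-up. In that time, laboratory-based incidence, grade and duration of neutropenia and thrombocytopenia cannot be systematically assessed. What remains depends on symptoms, known episodes, local practice or serious infection. This falls short of the stated objective and of the commitment to monitor safety by regular hematologic tests.

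The size is modest. The early late-onset period is covered by the Week 36 and Week 52 counts, and the primary endpoint is untouched. The fall from 10 to 5 per 100 patient-years is only a worst-case bound under constant hazard, no dropout or rescue cut, and no detection after Week 52. The conclusion rests on reading Protocol Appendix 2 as complete. Its footnotes run from a to f without a break and none concerns a hematology row, so nothing suggests a lost line.

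**What to change.** 1. **Protocol Appendix 2.** Add the existing central hematology panel (blood count with differential and platelets) to the Week 76, Week 104 and B-cell follow-up columns. Blood is already drawn at all of them, so the cost is one extra tube per visit and one table row. The counts would still be snapshots about six months apart and could miss short episodes. The SAP's Background section lists the Week 104 report as already issued, so in this trial the change can help only at visits still to come. It would also help any later protocol that reuses this schedule.

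2. **SAP Sections 4.8, 4.8.2 and 4.8.4.1.** Base hematology shift tables, and any neutropenia or thrombocytopenia rate per 100 patient-years, on data and time to the end of the Week 52 window (Day 364 + 60 = Day 424 under SAP Section 4.5). Show later counts separately, labelled as unscheduled or event-triggered, and state the limitation beside them, including in the post-Week-104 summary. Name the key safety events and define total exposure, since Section 4.8.2 does neither. This needs wording and programming but no new data. The downside is that quoted rates may look higher.

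3. **Protocol Sections 5.3.1 and 5.4.2.2.** Reconcile the two reporting periods for adverse events of special interest, so that the period the late data are meant to cover is clear.

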**Table 1 Classifications**

Class	Description
Class I	Minimal mesangial LN Normal glomeruli by light microscopy, but mesangial immune deposits by immunofluorescence
Class II	Mesangial proliferative LN Purely mesangial hypercellularity of any degree or mesangial matrix expansion by light microscopy, with mesangial immune deposits A few isolated subepithelial or subendothelial deposits may be visible by immunofluorescence or electron microscopy, but not by light microscopy
Class III	Focal LN Active or inactive focal, segmental or global endo- or extracapillary glomerulonephritis involving <50% of all glomeruli, typically with focal subendothelial immune deposits, with or without mesangial alterations
Class III (A)	Active lesions: focal proliferative LN
Class III (A/C)	Active and chronic lesions: focal proliferative and sclerosing LN
Class III (C)	Chronic inactive lesions with glomerular scars: focal sclerosing LN
Class IV	Diffuse LN Active or inactive diffuse, segmental or global endo- or extracapillary glomerulonephritis involving ≥50% of all glomeruli, typically with diffuse subendothelial immune deposits, with or without mesangial alterations. This class is divided into diffuse segmental (IV-S) LN when ≥50% of the involved glomeruli have segmental lesions, and diffuse global (IV-G) LN when ≥50% of the involved glomeruli have global lesions. Segmental is defined as a glomerular lesion that involves less than half of the glomerular tuft. This class includes cases with diffuse wire loop deposits but with little or no glomerular proliferation.
Class IV-S (A)	Active lesions: diffuse segmental proliferative LN
Class IV-G (A)	Active lesions: diffuse global proliferative LN
Class IV-S (A/C)	Active and chronic lesions: diffuse segmental proliferative and sclerosing LN
Class IV-G (A/C)	Active and chronic lesions: diffuse global proliferative and sclerosing LN
Class IV-S (C)	Chronic inactive lesions with scars: diffuse segmental sclerosing LN
Class IV-G (C)	Chronic inactive lesions with scars: diffuse global sclerosing LN

**Appendix 3 International Society of Nephrology/Renal Pathology Society (ISN/RPS)  
2003 Classification of Lupus Nephritis (cont.)**

